8.4 Administration of experimental and control interventions

Experimental Intervention („lidocaine group“)

Lidocaine 1% will be administered I.V., 1.5 mg/kg lean body mass will be given as bolus when general anesthesia steady state concentration is accomplished, 1.5 mg/kg lean body mass/h will be given as continuous infusion with beginning of surgical procedures and up to four hours from completion of surgery, or till transfer to surgical ward.

Control Intervention (“placebo group”)

The management of patients in the placebo group equals our current clinical routine and no standard treatment is withheld from this group of patients. This is specifically true for the analgesic regime.

Saline 0.9% will be administered I.V., 0.15 ml/kg lean body mass will be given as bolus when general anesthesia steady state concentration is accomplished, 0.15 ml/kg lean body mass/h will be given as continuous infusion with beginning of surgical procedures and up to four hours from completion of surgery, or till transfer to surgical ward.

8.5 Dose modifications

If SAE will be recognized, infusion of investigational product will be stopped and arrangements conducted to treat potential adverse effects and ensure patients` safety. The Principal Investigator will be informed about the incident within 24 hours.

8.6 Compliance with study intervention

Patients will be informed during preoperative anesthesiological consultation and give their informed consent. Patients denying informed consent will be excluded from the pool of selected patients. During consultation, patients will be informed about general study sequences, process of drug administration, differences between the interventional and placebo group and the postoperative sequence. The detailed version of patients' information is given in the appendix. In addition, general information about risk of anesthesia and perioperative adverse events are explained during the pre-anaesthesia visit and are part of the "Consent to Anaesthesia" ("Patienteneinwilligung") according to institutional practice.

8.7 Trial specific preventive measures

Apart from the study intervention, standard anesthetic technique will be used in all patients at the discretion of the attending anesthesiologist. Medication and treatment plans which are permitted before and/or during the trial include the medication and treatment plans listed in the „Kantonsspital St. Gallen – Standard Anästhesie“. Equipment and medication for resuscitation and treatment of adverse events occurring during and after anaesthetic procedures are available in all operation theatres, the PACU and intensive care unit according to institutional standards. In addition, trained personal is continuous available in these locations. Accordingly, no study specific measures are necessary. Vital parameters (blood pressure, pulse rate, oxygen saturation) will be recorded and possible deviations resulting in clinical relevant consequences treated immediately by attending anesthesiologist. Incidence of any potential AE, SAE due to application of IMPs will be documented and treated (e.g. local skin reactions, nausea, vomiting, dizziness, ear ringing, cardiac arrhythmia with relevant hemodynamic outcome or cardiac arrest) or adverse events related to opiates (e.g. hypoventilation).

8.8 Concomitant Interventions (treatments)

Apart from the study intervention, standard anesthetic technique and perioperative medication will be used in all the patients at the discretion of the attending anesthesiologist. Accordingly, different treatment options and drugs are allowed. These include current medical treatment options applied by the Kantonsspital St. Gallen. Patients will be in-

formed about treatment options during preoperative anesthesiological visit. Induction of anesthesia will be performed in line with the „Standard Anästhesie“ of the Kantonsspital St. Gallen. These treatments will have no impact on the effect of the IMPs. Postoperative pain management will be performed according to current clinical standards (Schmerzkarte KSSG).

8.9 IMPs / Medical Device Accountability

IMP Lidocaine will be provided by Streuli Pharma AG, Switzerland and IMP saline will be provided by Grosse Apotheke Dr. G. Bichsel AG, Switzerland. Storage and distribution will be organized by the pharmacy of the Kantonsspital St. Gallen, as well as prepackaging, assembly, blinding procedure and labeling. Adequate records about maintenance, shipment to the site, return or disposal of remaining or expired IMPs, physical location, dates of receipt, expiry, use and return, stock numbers and quantities received, used or destroyed will be recorded, referring to GMP. The pharmacy of the Kantonsspital St. Gallen is certified with the cantonal approval of manufacturing (kantonale Herstellungsbewilligung).

9. STUDY ASSESSMENTS

9.1 Study flow charts / table of study procedures and assessments

Please refer to appendix for a detailed graph of the study procedures and assessment plans.

9.2 Assessments of outcomes

Assessment of Pain

Pain will be assessed by the visual analogue scale (VAS) or the numeric rating scale (NRS), respectively, 0 indicating no pain and 10 maximal possible pain sensation. VAS/NRS scoring systems are validated and frequently used methods to evaluate variations in pain intensity. The VAS/NRS score will be recorded by trained nurse practitioners in the PACU, respectively on the surgical ward, once per hour during the first four hours after completion of surgery. Analysis of the primary outcome (any development of

VAS/NRS score > 3, in hourly measurements within the first four hours after completion of surgery) will be dichotomized accordingly. Thereafter, VAS/NRS score will be assessed by a patient questionnaire for self-evaluation and in addition by trained nurse practitioners during their daily round (10am and 2pm respectively +/- 30 minutes) during the first 48 hours after completion of surgery. Missing postoperative VAS/NRS scores, required for primary and secondary endpoints, will be handled as interpolation values, calculating an average score between last recorded scores before and after the missing value.

Secondary endpoints

- Average maximal pain intensity during first four hours and during 48 hours
- total amount of opiates as documented in the electronic anesthesia records during surgery and on PACU
- total amount of opiates applied on surgical ward, recorded in the charts. Values will be categorized in total amount in mg, average amount in mg/h and indexed amount in mg/kg bodyweight/h
- any event of postoperative nausea and vomiting (subdivided by event of no nausea (PONV = 0), event of nausea without vomiting (PONV = 1) and event of nausea with vomiting (PONV = 2)) during first 48 hours after completion of surgery
- time to first defecation after completion of surgery (quantified in hours)
- total time spent in hospital after completion of surgery (quantified in days)

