3.6 Standardized procedures

Since our institute cares for anesthesia in up to 150 patients per year in bariatric surgery, we want to optimize the outcome and postoperative analgesia for patients and guarantee a phase free of pain and other complications. The intervention is usually proceeded laparoscopically, with an average length of 120 minutes. Overweight patients with a mean BMI of 38 points, receive general anesthesia (TIVA and initial fentanyl application of 0.6 - 1.0 mg I.V.). After completion of surgery, patients are transferred to PACU for further observation and treatment. Emphasizing, these patients require almost double amount of opiates in the perioperative setting, than patients receiving laparoscopic appendectomy or hemicolectomy, as well as during the postoperative phase. The adverse effects of an increased opiate consumption like nausea, vomiting, hypopnea, pruritus and reduced gastrointestinal function are commonly aggravating the symptoms of pre-existing diseases like sleep apnea syndrome, reduced functional residual capacity, due to higher intraabdominal mass and thereby caused dyspnoea. Based on increased pain levels, these patients receive up to 1.0 mg fentanyl during the first four hours after completion of surgery to cope with pain. Additionally, PONV, induced by opiates, presents a major discomfort for these patients.

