5.2 Secondary outcome

Average experienced maximal pain during the first four hours and 48 hours (in hourly measurements on PACU and in eight-hourly measurements on surgical ward) is assessed by VAS/NRS score. The total amount of opiates (given during surgery and on PACU and administrated on surgical ward).

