8. STUDY INTERVENTION

8.1 General information

Patients will randomly be allocated either to the “lidocaine group“, or the “placebo group”. The only difference between both groups will be the implementation of a systemic lidocaine infusion during perioperative phase. All over management and techniques of anesthesia will be handled as described in the current “Standard Anaesthesie KSSG”. It includes detailed description of anesthesiological procedures for specific surgical interventions. Patients listed for bariatric surgery receive detailed information about anesthesiological techniques, course and management of adverse effects due to medical side effects or surgical complications during the preoperative anesthesiological consultation. On the day of surgery, the patient will receive premedication of 1 mg paracetamol p.o. one hour before planned intervention. Apart from the study intervention, standard anesthetic technique and pain management (related to practice of the anesthesiological standard of the Kantonsspital St. Gallen will be used in all the patients at the discretion of the attending anesthesiologist (use of alternative aminoamid local anesthetics, as additional analgesic will be prohibited during treatment and hospitalization of patients included to the study). After securing intravenous line, monitoring will be installed. Baseline parameters will be observed and recorded in the ACPDMS. Fentanyl ($\approx 0.002 \dots 0.003$ mg/kg) will be given intravenously two minutes before the induction of anesthesia in both groups. Airway management in patients with a mean BMI > 35 kg/cm² is performed by fiberoptic nasal intubation in awake condition. Nasal drops (0.25 ml cocainehydrochloride 10%) will be applied and transcrucial application of 2 ml lidocaine 1% for anesthesia of the upper airway will be performed before advancing the fiberscope into the trachea. As soon as vocal cords are crossed, induction of general anesthesia will be induced with etomidate 0.2 mg/kg bodyweight. Thereafter the nasotracheal tube is placed. Anesthesia will be maintained by target controlled infusion of propofol 1% and remifentanyl 40 μ g/ml according to institutional standards in all patients. Neuromuscular blockade will be achieved by bolus followed by continuous administration of rocuronium as clinically necessary.

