Study intervention: Patients in the “lidocaine group” will receive 1.5 mg/kg lean body mass of lidocaine 1% bolus intravenously after induction of general anesthesia (as soon

as general anesthesia's steady state is accomplished), followed by a continuous infusion of lidocaine 1% with 1.5 mg/kg lean body mass/h during surgery and continued for four hours after completion of surgery or until the discharge from the PACU, whatever comes first. Patients in "placebo group" will receive 0.15 ml/kg lean body mass of saline 0.9% bolus I.V. after induction of general anesthesia (as soon as general anesthesia's steady state is accomplished), followed by continuous infusion of NaCl 0.9% I.V. with 0.15 ml/kg lean body mass/h during surgery and continued for four hours after completion of surgery or until the discharge from the PACU, whatever comes first. Maintenance of general anesthesia and optional application of additional opiates for pain treatment (fentanyl 0.1 - 0.2 mg as an intravenous bolus) during surgery is under discretion of the attending anesthesiologist and is related to the practice of standardized pain management and will be equal in both groups. Similarly, postoperative treatment in the PACU and further on the surgical ward, are under discretion of the clinically responsible physicians, relating to current practice of standardized pain management at the Kantonsspital St. Gallen (Schmerzkarte KSSG).

A detailed graphical version of study sequences is provided in german as follows:

Periode	Ort	Intervention	Details
Anmeldung	Studien- koordination	Screening	Ein- / Ausschlusskriterien evaluieren
		erfüllt	
PAS Termin	PAS	Informed consent	Aufklärung und Einwilligung durch Patienten
		erfüllt	
PAS Termin	PAS	Randomisierung	Zuteilung zur Gruppe Lidocain oder Placebo
OP Datum	OPS 03	Intervention COALAS	- IMP Bolus ab AN steady state - anschliessend Beginn IMP Perfusor - Datenerfassung ACPDMS (Medis, Vitalparameter) - AE, SAE, ADR erfassen
		Transfer	
POD 0	PACU	VAS Monitoring VAS Evaluationsbogen	- IMP Perfusor bis 4 Std. ab "OP-Ende" od. Transfer auf Abteilung - VAS 1.,2.,3.,4. Std. - Datenerfassung ACPDMS (Medis, Vitalparameter) - Prim./Sek. Variablen im CRF erfassen - AE, SAE, ADR erfassen
		Transfer	
POD 0	ABTEILUNG	VAS Monitoring 2pm, 10pm Studiensite 10am, 2pm	- Erinnerung des Pat. durch Pflege- Studienpersonal - Prim./Sek. Variablen im CRF erfassen - AE, SAE, ADR erfassen

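### Total opiate consumption is defined in milligrams with no rule for combining different opiates, so the combined total cannot be read as opioid consumption

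*Combined protocol and SAP*

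**What the plan says.** Section 4.2 names total opiate consumption, together with average maximal pain intensity, as what lidocaine should reduce over the first four hours and over 48 hours. Section 5.2 describes the outcome as a single amount of opiates "given during surgery and on PACU and administrated on surgical ward".

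Section 9.2 splits this into two items. The first is the "total amount of opiates as documented in the electronic anesthesia records during surgery and on PACU", with no unit. The second is the amount given on the ward, and it carries the only statement of units: "Values will be categorized in total amount in mg, average amount in mg/h and indexed amount in mg/kg bodyweight/h".

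More than one opiate is involved:

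- **Remifentanil.** Section 8.1 says: "Anesthesia will be maintained by target controlled infusion of propofol 1% and remifentanyl".
- **Fentanyl.** Section 8.1 provides for it before induction and as optional intraoperative doses ("fentanyl 0.1 - 0.2 mg as an intravenous bolus"). Section 3.6 says that "these patients receive up to 1.0 mg fentanyl during the first four hours after completion of surgery to cope with pain".
- **Ward opiates.** Sections 8.1 and 8.8 refer to the hospital's pain standard. No ward drug is named.

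Section 10.5 adds only an unpaired parametric or non-parametric test for continuous data. No section gives an equianalgesic conversion, lists the opiates that count, says whether remifentanil is included, or asks for results by drug.

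**The concern.** Milligrams of opiates that differ in potency or route are not a common scale. In a sum of raw milligrams, the drug given in the largest mass dominates, whatever its share of the analgesia. Dividing by hours or by body weight does not change this.

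Two totals are exposed. The surgery and PACU total pools two named opioids, one of which maintains anaesthesia and so depends on infusion target and length of surgery. The 48-hour total spans PACU and ward, and so may add a ward opiate of quite different potency. A real fall in PACU fentanyl could be lost in variation of the ward drug, and a difference in drug mix could look like a difference in consumption. Opioid sparing is part of the trial's stated rationale (sections 3.5 and 3.6), so a result on this outcome is likely to be cited.

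**Working it through.** **The plan's own figures.** The protocol gives no effect size, SD or power for opiate consumption, so there is nothing to reproduce for this endpoint. The sample size for the primary endpoint (65% against 35%, two-sided 0.05, 90% power) reproduces as 63 per group with continuity correction, and 126/0.9 = 140. It does not depend on this point.

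**1. Weight of PACU fentanyl in a combined total.** Input from section 3.6: 1.0 mg fentanyl, the upper figure. Assumed: 10 mg of a ward opiate that is *r* times less potent per mg. To isolate the effect, only these two amounts are compared.

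- Raw mg: 1.0/(1.0 + 10) = 9%
- Converted, *r* = 10: 1.0/(1.0 + 10/10) = 50%
- Converted, *r* = 100: 1.0/(1.0 + 10/100) = 91%
- *r* = 1: 9% on both scales, so no distortion

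**2. Remifentanil in the surgery and PACU total.** From section 3.6: 120 minutes average surgery; fentanyl 0.6–1.0 mg initially plus up to 1.0 mg in the first four hours, i.e. 1.6–2.0 mg. Assumed: remifentanil 0.1–0.3 µg/kg/min and 60–110 kg (the protocol specifies a target-controlled infusion without rates).

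- Low: 0.1 × 60 × 120/1000 = 0.72 mg; share 0.72/(0.72 + 2.0) = 26%
- High: 0.3 × 110 × 120/1000 = 3.96 mg; share 3.96/(3.96 + 1.6) = 71%

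Optional intraoperative boluses are left out and would lower the share. Less than 1.0 mg fentanyl in PACU would raise it.

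**3. Can the direction reverse?** Assumed means: lidocaine 0.7 mg fentanyl + 11 mg ward opiate; placebo 1.0 mg + 10 mg.

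- Raw mg: 11.7 against 11.0, unfavourable to lidocaine.
- In ward-drug equivalents: 0.7*r* + 11 against 1.0*r* + 10. Lidocaine is lower when 0.3*r* > 1, i.e. *r* above about 3.3. At *r* = 10 the totals are 18 and 20; at *r* = 50 they are 46 and 60.

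**4. Loss of power.** Assumed: a true 0.3 mg reduction in fentanyl, fentanyl SD 0.3–0.5 mg, an unaffected and uncorrelated ward opiate with SD 5–20 mg, 63 per group. Power for rejection in lidocaine's favour is Φ(δ/(σ√(2/63)) − 1.96). On the raw scale δ = 0.3 and σ² = SD_F² + SD_W². On the converted scale δ = 0.3*r* and σ² = (*r*·SD_F)² + SD_W².

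| *r* | Raw mg | Converted |
|---|---|---|
| 1 | 3–5% | 3–5% |
| 10 | 3–5% | 13–82% |
| 50 | 3–5% | 75–100% |
| 100 | 3–5% | 88–100% |

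On the raw scale fentanyl supplies 0.02% to 1% of the variance.

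**The case against.** The strongest reply is that the plan never says milligrams of different drugs are to be added. The sentence on units belongs to the ward item of section 9.2, surgery and PACU form a separate item, and PACU fentanyl need not enter a ward total. A four-hour total would largely exclude ward drugs. If the hospital standard uses one opiate by one route on the ward, ward milligrams are sound. Ward drug, dose and potency ratio are all assumed here. The remifentanil share is not in itself a potency distortion, because the documents give no ratio between remifentanil and fentanyl. And under blinded randomisation, differences in ward drug choice unrelated to treatment add noise, not systematic bias.

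Much of this stands. A reader might infer that the protocol lays down an explicit rule to sum raw milligrams; it does not. That reading follows from the single total in section 5.2, the 48-hour objective in section 4.2 and the absence of any other rule. Steps 1, 3 and 4 apply only to a total that joins PACU and ward. Step 2 shows a mixture of anaesthetic maintenance and analgesic demand.

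The reply does not remove the problem. The surgery and PACU item pools two named opioids whatever happens on the ward, and a 48-hour total cannot be formed without adding phases.

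**Conclusion.** The point holds for combined totals. With mass as the only stated scale and no combining rule, a total across different opiates is not interpretable as opioid consumption and may hide or reverse a difference. The sizes are illustrations: 9% against 50–91% rests on the assumed ward dose and a potency ratio of 10 to 100, and the remifentanil share of about 26–71% rests on assumed rates and weights. The documents do not allow the actual distortion to be calculated.

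Two stronger readings are not supported. One is that this is the main secondary endpoint: section 4.2 names it beside maximal pain intensity without ranking them. The other is that the endpoint fails to measure opioid use at all: where one drug is given by one route, milligrams are a valid measure. The primary endpoint and sample size are untouched. The change should be made, as a cheap improvement to a secondary endpoint.

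**What to change.** In sections 5.2 and 9.2:

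- List the opiates that count and the phases that each total covers.
- Convert each opiate, by drug and route, to intravenous morphine equivalents with one sourced table fixed before unblinding.
- Analyse the 4-hour and 48-hour totals on that scale.
- Report intraoperative remifentanil separately, outside the total.
- Show amounts by phase and by drug, so that readers can apply other factors.

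The cost is a wording change and one table, made by amendment as section 10.7 requires. Doses should already be available from the electronic anaesthesia records and the ward charts, and patient care does not change. The drawback is that conversion factors are approximate; the drug-specific amounts let a reader judge how far the result depends on them. Choosing the factors, or deciding on remifentanil, after unblinding would make the result data-dependent.

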9.3 Assessments of safety outcomes

Vital parameters (blood pressure, pulse rate, oxygen saturation) will be recorded digitally by the electronic acute care patient data management system (ACPDMS) during the peri- and postoperative phase and according to institutional standards.. During the entire surgical and anaesthetic procedure and in the PACU trained personnel will be present monitoring vital parameters and the patient clinical status. Every deviation to normal course will be treated and recorded according clinical standards of the institution. SAE related to the administration of the IMP will cause an immediate cessation of the drug administration and will be reported to the Sponsor Investigator not later than 24 hours after the event.

9.4 Procedures at each visit

Each patient will be visited after surgical treatment and transfer to PACU/ICU by a study nurse or the Study Investigator. The VAS/NRS score (registration of any development of VAS/NRS score > 3) will be assessed by trained nurse practitioners in the PACU/ICU in hourly measurements during the first four hours after completion of surgery, respectively until discharge to the surgical ward. Thereafter, VAS/NRS score will be assessed by a patient questionnaire for self-evaluation and in addition by trained nurse practitioners during their daily round (10am and 2pm respectively ± 30 minutes) during the first four hours and during 48 hours after completion of surgery. VAS/NRS scores and vital parameters will be recorded. Incidental questions about upcoming study process will be answered. Infusion of the investigational product will be stopped four hours after the end of surgery (or before the transfer of the patient from the PACU to the surgical ward, whichever occurs first). Pain evaluation will take place every eight hours by recording the maximum VAS/NRS score experienced within this period. Recording of VAS/NRS scores will be stopped at 2pm respectively ± 30 minutes on second postoperative day. Completion of study investigation will be finalized by collecting the study documents at study nurses final visit on second postoperative day at 2pm respectively ± 30 minutes.

10. STATISTICAL METHODS

10.1 Statistical considerations

Determination of sample size was performed by retrospective analysis of 50 patients' records, listed for bariatric surgery at the Kantonsspital St. Gallen in the year 2015. Experienced pain score determined as VAS/NRS score, amount of opiates required and occurrence of PONV in the postoperative periode were reviewed and examined. Compared to other laparoscopically performed surgeries, patients undergoing a bariatric intervention reported higher postoperative pain levels and required more opiates. In total, 35 of 50 patients showed an average VAS/NRS score > 3 during the first four hours after surgery. This accounts for 65% regarding the whole population examined. Average VAS/NRS score after eight hours was > 3 in 35% of patients.

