Control Intervention

“placebo group”

- *0.15 ml/kg lean body mass saline 0.9% bolus I.V. as general anesthesia steady state concentration is accomplished*
- *0.15 ml/kg lean body mass/h saline 0.9% I.V. with beginning of surgical procedure*
- *after completion of surgery: transfer to PACU, pain evaluation (VAS/NRS score questionnaire) for 48 hours, nurse –based pain treatment as appropriate*
- *duration of intervention: saline infusion up to four hours from completion of surgery, or till transfer to surgical ward*

Number of Participants

63 participants per group + 10% to account for drop-outs (sum. 140 patients),

χ^2 test (allocation of VAS/NRS score ≤ 3 to 65% of interventional group), p-value 0.05, power 90%

Study Duration

Estimated duration for the main investigational plan (from start of screening of first participant to last participant processed and finishing the study) will be approximately two years

Investigator

[name]. med. [name]

Kantonsspital St. Gallen

Klinik für Anästhesiologie, Intensiv-, Rettungs- und Schmerzmedizin

Study Centre

Single center, Kantonsspital St. Gallen

Klinik für Anästhesiologie, Intensiv-, Rettungs- und Schmerzmedizin

[name]

[name]

Switzerland

Statistical Considerations:

Sample size of 63 subjects per group was estimated to achieve 90% power and to detect 65% redistribution of VAS/NRS score ≤ 3 in favour of the "lidocaine group".

To account for drop-outs, 140 subjects were recruited and randomized.

GCP Statement

[figure not shown]
This study will be conducted in compliance with the protocol, the current version of the Declaration of Helsinki, the ICH-GCP as well as all national legal and regulatory requirements.

Abbreviations

AE Adverse Events
ASA American Society of Anesthesiologists
BMI Body Mass Index
CA Competent Authority (e.g. Swissmedic)
CEC Competent Ethics Committee
CRF Case Report Form
eCRF Electronic Case Report Form
CTCAE Common terminology criteria for adverse events
EKOS Ethikkommission Ostschweiz
GCP Good Clinical Practice
GMP Good Manufacturing Practice
HFG Humanforschungsgesetz (Law on human research)
HMG Heilmittelgesetz
HRA Federal Act on Research involving Human Beings
ICU Intensive Care Unit
IL-6 Interleukin-6
IMC Intermediate Care Unit
IMP Investigational Medicinal Product
LBM lean body mass
MD Medical Device
MEGX Monoethylglycinexylidide
NMDA N-Methyl-D-Aspartat
NRS Numeric Rating Scale
OSA obstructive sleep apnea

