5. STUDY OUTCOMES

5.1 Primary outcome

Any development of VAS/NRS score > 3 , in hourly measurements within the first four hours after completion of bariatric surgery.

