10.2 Hypothesis

Null hypothesis: perioperative treatment of patients undergoing bariatric surgery with lidocaine has no impact on postoperative quality of analgesia.

Alternative hypothesis: perioperative treatment of patients undergoing bariatric surgery with lidocaine reduces the proportion of patients suffering from more intensive pain (any development of VAS/NRS score > 3 , in hourly measurements) within the first four hours from currently 65% to 35%.

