10.3 Determination of Sample Size

With an expected postoperative VAS/NRS score (any development during first four hours after completion of surgery) of > 3 points in patients undergoing elective bariatric surgery of 65% in the control group, the expected frequency of VAS/NRS score ≤ 3 is 65% in the interventional group. A two group test with a 0.05 two-sided significance level will have 90% power to detect a redistribution of VAS/NRS score ≤ 3 points in favour of interventional group when the sample size in each group is 63. Assuming a 10% dropout rate, 140 subjects will be recruited and randomized. Sample size was calculated according to Jaykaran et al. with a sample size calculation for χ^2 tests using web-based sample size calculator on biomath.info. (55, 56)

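### The 65% control rate behind the sample size disagrees with its own count (35 of 50 is 70%) and comes from an average-score measure, not the any-hourly-score primary outcome

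*Combined protocol and SAP*

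**What the plan says.** Section 10.1 says that the sample size was determined from a retrospective review of 50 bariatric records from 2015. It reports: "In total, 35 of 50 patients showed an average VAS/NRS score > 3 during the first four hours after surgery. This accounts for 65" per cent of the whole population examined. It adds a later time point: "Average VAS/NRS score after eight hours was > 3 in 35% of patients".

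Section 5.1 defines the primary outcome as any score above 3, "in hourly measurements within the first four hours after completion of bariatric surgery". Section 10.2 and the synopsis hypothesis express the planned effect on that outcome as a reduction "within the first four hours from currently 65% to 35" per cent. Section 10.3 uses the same control rate, opening "With an expected postoperative VAS/NRS score (any development during first four hours after completion of surgery) of > 3 points", and gives the lidocaine arm as its complement: "the expected frequency of VAS/NRS score ≤ 3 is 65% in the interventional group". The power statement is: "A two group test with a 0.05 two-sided significance level will have 90% power to detect a redistribution", with 63 patients per group, raised to 140 in total for 10% dropout.

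The synopsis entry on number of participants repeats the complement ("allocation of VAS/NRS score ≤ 3 to 65% of interventional group"). The synopsis statistical considerations describe the effect as a redistribution of 65%.

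**The concern.** Two things do not fit. First, the count and the percentage in 10.1 contradict each other, and the text does not show whether the numerator, the denominator or the percentage is wrong. Second, the review measured whether a patient's average four-hour score exceeded 3, while the trial counts a patient as soon as one hourly score exceeds 3. The second event is easier to reach. Sections 10.2 and 10.3 nevertheless present 65% as the current rate of the second event, which the review as described did not tabulate.

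At stake is the traceability of the trial's only power claim. If the trial is negative, readers will judge it against the stated 90%, and one of the two rates behind that figure cannot be matched to its source.

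**Working it through.** **The count (10.1).** 35/50 = 0.70 (Wilson 95% interval 56.2% to 80.9%). Conversely, 0.65 × 50 = 32.5, not a whole number of patients. A count of 35 at 65% would need 35/0.65 = 53.8 records, but 10.1 says 50.

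**The measure (10.1 against 5.1, 10.2, 10.3).** If every score in the window is 3 or less, the average is 3 or less. So an average above 3 implies at least one score above 3, and in the same records the any-score rate is at least the average-score rate: at least 70% if the count of 35 is right, at least 65% if the percentage is. This holds only if the averaged scores are the ones the endpoint uses, and 10.1 does not say that they were hourly.

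**The plan's own sample size.** Inputs from 10.3: p1 = 0.65, p2 = 0.35, two-sided 0.05 (z = 1.960), 90% power (z = 1.2816), difference d = 0.30, mean rate 0.50.

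- Uncorrected: n = [1.960 × √(2 × 0.5 × 0.5) + 1.2816 × √(0.65 × 0.35 + 0.35 × 0.65)]² / 0.30² = (1.3859 + 0.8645)² / 0.09 = 56.3.
- With continuity correction: n/4 × [1 + √(1 + 4/(n × d))]² = 14.07 × (1 + 1.1122)² = 62.8, so 63 per group.
- Dropout: 63/0.9 = 70 per group, 140 in total.

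The plan's 63 and 140 both reproduce.

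**Power at 63 per group.** Exact power of the two-sided chi-square test, enumerating both binomial distributions with critical value 3.8415. Every pair except 65 v 35 contains at least one assumed rate.

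| Control v lidocaine (%) | Why this pair | Power without / with continuity correction (%) |
|---|---|---|
| 65 v 35 | as planned | 93.7 / 91.5 |
| 70 v 40 | 70% control, 30-point difference held | 94.0 / 91.7 |
| 70 v 35 | 70% control, lidocaine rate held | 98.4 / 97.6 |
| 65 v 40 | difference five points smaller, from the lidocaine side | 82.8 / 78.4 |
| 60 v 35 | difference five points smaller, from the control side | 82.8 / 78.4 |
| 80 v 50 | higher any-score rate, difference held | 95 / 93 |
| 80 v 43.1 | higher any-score rate, risk ratio 35/65 held | 99 / 99 |
| 80 v 53.7 | higher any-score rate, odds ratio held | 89 / 85 |

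The planned odds ratio is (0.35/0.65)/(0.65/0.35) = 0.290. At a control rate of 80% it gives lidocaine odds of 4 × 0.290 = 1.160, which is 53.7%.

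**The case against.** The strongest reply is that nothing in the design changes. The arithmetic from 65% v 35% is right, 70% in place of 65% costs no power, and a higher any-score control rate lowers power in only one of the three ways of carrying the effect over. The effect size is a design assumption, which sponsors may set. All of this stands, and it limits the point to the planning figure and its source.

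Four stronger readings are tempting, and the documents support none of them.

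- *The trial is underpowered.* No combination taken from the documents gives power below 90%. The lower figures above come from assumed rates.
- *The review supports neither planning rate.* It covers the same centre, type of surgery, scale and four-hour window, and bounds the control rate from below if the same scores were used. For lidocaine, section 3.2 cites a meta-analysis finding less pain in the first four hours; only the size of the effect lacks a stated source.
- *Power depends mainly on the lidocaine rate.* It does not: 65 v 40 and 60 v 35 give identical power.
- *The eight-hour 35% is itself an impossible count, or was reused as the lidocaine rate.* That sentence gives no denominator, so it may rest on fewer than 50 records, and nothing links it to the treated arm.

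What the reply does not remove is that 10.1 contradicts itself and that 65% is presented as the current rate of something the review, as described, did not count.

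**Conclusion.** The point holds as an error in a planning input, not as a shortfall in sample size. The stated control rate is five percentage points below its own count and belongs to a different measure from the primary outcome. On the cited records the any-score rate is probably higher than planned, but by how much cannot be told from the documents; the lower bound assumes that the averaged scores are the hourly ones.

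The numbers 63 and 140 are correct for the rates used. Replacing 65% by 70% leaves power at 94.0/91.7% with the 30-point difference held, or 98.4/97.6% with lidocaine at 35%. Power does depend on both rates: a difference five points smaller, from either side, brings it to 82.8/78.4%. A higher control rate lowers it only if the odds ratio is the quantity that carries over. The text should be corrected because the 90% claim relies on it. The unsourced 35% lidocaine rate is a documentation point only.

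**What to change.** - In 10.1, reconcile the count, the denominator and the percentage with the source records.
- Re-tabulate those records on the actual endpoint, any hourly score above 3 in the first four hours, and use that rate in the synopsis, 10.2 and 10.3. If hourly scores are not available, label the control rate an assumption.
- Restate the power at 63 evaluable patients per group with the corrected control rate.
- Minor: say that the 35% lidocaine rate is an assumption. In the synopsis statistical considerations, replace the wording about a 65% redistribution with the two rates, as the synopsis hypothesis already does.

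The cost is a recount of existing records and text edits. The stated power may become slightly less favourable. No increase in enrolment is asked for, and the endpoint, test and significance level stay as they are.
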